3. STUDY POPULATION

3.1. DESCRIPTION OF THE POPULATION

The subjects were patients suffering from fibromyalgia, recruited during their treatment by the Centre d'Evaluation et de Traitement de la Douleur de Vendée (CETD) at the sites of La Roche sur Yon, Montaigu and Luçon, as well as at the CHU in Nantes.

The study plans to include 140 patients with the aim of achieving 126 randomised patients. Inclusion will stop when the potential number of randomised patients is reached. (see paragraph 5 statistics).

3.2. INCLUSION CRITERIA

- Patient of legal age,
- Diagnosis of fibromyalgia (Häuser et al., 2017):

$4 < \text{WPI} < 6$ and $\text{SSS} \geq 9$ **OR**

$\text{WPI} \geq 6$ and $\text{SSS} \geq 5$ **AND**

pain present in **at least 4** of the 5 regions of the body (5 regions = 4 dials + the axis).

- Patient with FIQR $\leq 59/100$
- Patient can be followed for 12 months in the CETD,
- Patient able to follow the physical activities proposed by "Siel Bleu", on a physical and organisational level,
- Patient with a smartphone and/or computer (mac/pc) with an internet connection allowing the use of a monitoring application linked to the activity tracker,
- Patient with the ability to understand the protocol and who has given consent to participate in the study,
- Patient with social security coverage.

3.3. *NON-INCLUSION CRITERIA*

- Patient participating in an interventional trial within 3 months of inclusion,
- Pregnant or breastfeeding women, or women with the potential to conceive without effective contraception,
- Patient who is a minor, under guardianship, curatorship or deprived of liberty,
- Patient unable to follow the protocol, as judged by the investigator, or unwilling to use the digital applications,
- Patients with contraindications to physical activity,
- Patients who have already taken part in the physical activities offered by "Siel Bleu".

3.4. *FEASIBILITY*

An investigation with the CETD-Vendée team, cross-checked with the files of the "Siel Bleu" association network, showed an active file of 4 new patients per week on average, i.e. 200 new patients per year.

The Nantes University Hospital estimated that it would be possible to include an active file of 24 patients per year, given their patient base and the resources required for this project.

With a 20% refusal rate, we would have 179 patients included in the year.

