2.2. OBJECTIVES AND SECONDARY EVALUATION CRITERIA

Secondary objectives

Compare between the 2 randomisation arms:

1. The evolution of pain intensity between the beginning of the treatment (D0), at 6 months (M6) and at 12 months (M12),
2. The presence of neuropathic pain and its evolution,
3. The evolution of isochrony between a physically executed and mentally simulated movement (Moseley, 2004; Moseley et al., 2008)
4. The evolution of anxiety and the presence of signs of the depressive series
5. The evolution of pain on muscle compression

6. The severity of the symptoms
7. Monitoring physical activity with activity trackers
8. The evolution of lean body mass measured on an impedance scale
9. The evolution of kinesiophobia
10. Changes in quality of life between the start of treatment (D0) and 12 months (M12)
11. Continuity of physical activity after the end of coaching

Secondary evaluation criteria

1. EVA at D0, M6 and M12
2. DN4 questionnaire score ≥ 4 at D0, M6 and M12
3. Difference between the duration of the performed movement and the imagined movement of picking up a magazine from a table at D0, M6 and M12
4. Hospital Anxiety and Depression scale (HAD) at D0, M6 and M12
5. Widespread Pain Index (WPI) (Häuser et al., 2017; Wolfe et al., 1990) at D0, M6 and M12
6. Symptom Severity Scale (SSS) (Häuser et al., 2017; Wolfe et al., 1990) at D0, M6 and M12
7. Percentage of success in achieving goals each month (M1-M12) as measured by activity tracker
 - (Duration in minutes per month at least 70% of the theoretical maximum heart rate $\times 100 / 240$ minutes
 - (4 weeks \times 60 minutes recommended = 240 minutes)
8. Percentage and weight of lean mass measured on an impedance scale at D0, M6 and M12
9. Tampa self-questionnaire (Knapik, Saulicz, & Gnat, 2011) at D0, M6 and M12
10. FIQR at D0 and M12 and EQ5D-5L at D0, M6 and M12
11. Level of physical activity between the groups between M6 and M12
 - (the duration in minutes per month between 50 and 60, between 60 and 70, between 70 and 80, between 80 and 90, and between 90 and 100% of the theoretical maximum heart rate measured with the activity tracker)

Exploratory secondary objective

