The isochrony between executed and imagined movement is a test inspired by the work of Moseley (2004) showing an alteration in the temporality of imagined movement in chronic pain patients. Patient positioning: initially, the patient has the upper limb and hand at the side of the body, with the feet 30cm from a table. A magazine is positioned by the operator flat, at the edge and not protruding from the table. First, the operator will ask the patient, "On my 'go' signal, you will take the magazine lying flat in front of you with your dominant hand and bring the limb back along your body at your comfort speed. When you have brought your limb back, you will say "stop". I will stop the clock at your end stop. This movement is to be done twice. The operator will note the 2 times in seconds and hundredths. In a second step, the operator will ask the patient: "At my starting "top", you will, without actually doing it and without moving, imagine taking with your dominant hand the magazine lying flat in front of you

and imagine bringing the limb back along your body at your comfort speed. When you have imagined bringing your limb back, you will say "stop". I will stop the clock at your end stop. This movement is to be done twice. The operator will note the 2 times in seconds and hundredths.

The Hospital Anxiety and Depression scale (HAD, Appendix 8) is a screening instrument for anxiety and depressive disorders. It consists of 14 items rated from 0 to 3. Seven questions relate to anxiety (total A) and seven others to the depressive dimension (total D), thus making it possible to obtain two scores (maximum score for each score = 21) (Zigmond & Snaith, 1983).

The Widespread Pain Index (WPI, Appendix 9) is a score given by the patient according to the number of affected areas (Häuser et al., 2017)

The Symptom Severity Scale (SSS, Appendix 10) is scored by the patient and includes headache, pain, cramp in the abdomen and depression (Häuser et al., 2017)

The percentage of target attainment will be calculated by averaging the attainment of monthly results, compared to clinical practice guidelines from the results recorded by the use of activity trackers

⇒ Duration in minutes per month at least 70% of the theoretical maximum heart rate x100 / 240 minutes
(4 weeks x 60 minutes recommended = 240 minutes)

The percentage (%) and dry mass (in kg) of lean mass will be measured on an impedance scale

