4.5. STUDY SCHEDULE

TIMETABLE OF THE STUDY

Actions	J0 Inclusion visit	Between D0 and M6	M6	Between M6 and M12	M12
Patient information	X				
Collection of written consent	X				
Background	X				
Randomisation	X				
Clinical examination and questionnaires ¹	X		X		X
Encouragement to continue physical activity			X		
Physical activity with activity trackers		X	X	X ²	X ²
Analgesic treatments	X		X		X
Adverse events		X	X	X	X

¹EVA, DN4, HAD, WPI, SSS, impedance measurement, Tampa, FIQR, EQ-5D-5L

² Depending on the patient's choice

4.6. *IDENTIFICATION OF ALL SOURCE DATA NOT IN THE MEDICAL RECORD*

- Physical activity: practice at inclusion and type of activity
- Questionnaires: FIQR, DN4, Tampa, HAD, WPI, SSS, EQ-5D-5L
- EVA
- Physical activity during the study according to the randomisation arm (% success)
- Impedance measurement

4.7. *RULES FOR STOPPING A PERSON'S PARTICIPATION*

Criteria for premature termination of a person's participation in research

Any patient included in the protocol who no longer wishes to participate will be prematurely withdrawn from the study as soon as the request is made.

For the modalities and duration of the follow-up of the early leavers, see the statistical section.

- Withdrawal of patient consent at any time during the study, before publication of results.
Right to object to the use of the data at any time during the study, before publication of the results

Procedures for premature termination of a person's participation in research

For details of how to use the data of people who stopped the study prematurely, see the statistics section.

Criteria for stopping part or all of the research (excluding biostatistical considerations)

Part or all of the study may be stopped permanently or temporarily by decision of the ANSM, the CPP or the study sponsor.

A written confirmation will be sent to the coordinating investigator of the study (specifying the reasons for premature termination) and to the principal investigator of each centre if applicable.

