All variables will be described globally and by group. The description will include the numbers and percentages of modalities for qualitative variables and the minimum, maximum, mean, standard deviation and median for quantitative variables.

Main criterion

The patients' quality of life will be measured using the FIQR questionnaire at D0, M6 and M12. The evolution of the score at 6 and 12 months will be characterised by a graph and compared between the 2 groups using a linear regression model taking into account the baseline score at D0, the time effect, the "time*group" interaction and the repeated nature of the data.

The comparison of the evolution of the score at M6 will be tested from the M6 contrast.

Secondary criteria

The evolution of pain will be graphically characterised and compared using a mixed linear regression model taking into account the baseline data of the D0 score and the repeated nature of the data.

Neuropathic pain will be assessed using the DN4 questionnaire score. It will be compared between the two groups using a mixed generalized linear regression model taking into account the repeated nature of the data.

The evolution of the isochrony will be characterised graphically and compared using a mixed linear regression model taking into account the baseline data J0 and the repeated nature of the data.

The evolution of anxiety will be assessed from the total HAD score and compared between the two groups using a mixed linear regression model taking into account the baseline D0 score and the repeated nature of the data.

The evolution of pain on muscle compression will be assessed from the total WPI score and compared between the two groups using a mixed linear regression model taking into account the baseline score on D0 and the repeated nature of the data.

The severity of symptoms will be measured from the SSS score and compared using a mixed linear regression model taking into account the baseline data of the D0 score and the repeated nature of the data.

Physical activity monitoring will be collected every month until M12. Each month, the percentage of goal achievement will be calculated. The average percentage of success will be plotted and compared between the 2 groups using a mixed linear regression model taking into account the repeated nature of the data.

The evolution of lean body mass will be collected at D0 M6 and M12 and compared using a mixed linear regression model taking into account the repeated nature of the data.

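### The tracker goal-attainment model (secondary criterion 7) leaves out the physical activity already recorded at inclusion, which costs precision on a secondary endpoint

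*Combined protocol and SAP*

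**What the plan says.** **Eligibility (sections 3.2 and 3.3).** Two non-inclusion criteria concern exercise. One is "Patients who have already taken part in the physical activities offered by 'Siel Bleu", with no time window or amount. The other is "Patients with contraindications to physical activity". Nothing limits current exercise done alone or with another provider.

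**Data collected (section 4.6).** The source data include "Physical activity: practice at inclusion and type of activity". The format is not given.

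**Endpoint (sections 2.2 and 4.3).** Criterion 7 is "Percentage of success in achieving goals each month (M1-M12) as measured by activity tracker". The formula is "Duration in minutes per month at least 70% of the theoretical maximum heart rate x100 / 240 minutes", with the goal derived as "4 weeks x 60 minutes recommended = 240 minutes". No upper limit is stated. The schedule in section 4.5 starts tracked activity after D0, so there is no tracker baseline.

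**Analysis (section 5.2).** For criterion 7, "The average percentage of success will be plotted and compared between the 2 groups using a mixed linear regression model", and the only feature then named is the repeated nature of the data. By contrast, the pain model is described as "taking into account the baseline data of the D0 score and the repeated nature of the data". The FIQR, isochrony, HAD, WPI, SSS, Tampa and EQ-5D-5L models also name the D0 value. The DN4 and lean-mass models do not, but both outcomes are at least measured at D0. For criterion 11 (minutes per heart-rate zone between M6 and M12), section 5.2 describes no model.

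**The concern.** Criterion 7 measures how much a patient exercises, not how much that has changed. With no D0 value, habit and programme effect are mixed in each patient's score. Section 1.1 describes usual fibromyalgia care as including exercise, so some patients may well be active at entry.

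Two things are at stake. First, spread in prior activity becomes unexplained between-patient variance in the comparison of arms. Second, if one arm happens to receive more active patients, part of the observed difference in goal attainment reflects that, and the planned model has no term to correct for it. The variable that could absorb some of both is already on the list of data to collect.

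**Working it through.** **Inputs from the documents.** Goal: 4 weeks × 60 min = 240 min per month, which reproduces the protocol's figure. Aerobic amount cited in section 1.1: 20 min, two to three times a week at 70–80% of theoretical maximum heart rate, so 40 to 60 min per week. Planned randomised total: 126 in a 1:1 ratio, so 63 per arm.

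**Step 1: score from habit alone.** Score = minutes per week × 4 × 100 / 240.

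| Min/week at ≥70% | Score |
|---|---|
| 20 | 33% |
| 40 | 67% |
| 60 | 100% |
| 80 | 133% |

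A patient already at the cited amount therefore scores 67% to 100% with no change in behaviour. This requires that the exercise reaches the intensity threshold, that it continues, and that the tracker is worn for it. The documents do not say whether exercise outside the programme is to be recorded, and section 4.5 leaves tracked activity after M6 to the patient's choice.

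**Step 2: chance imbalance (illustration).** The share p of patients active at entry is not in the documents; 10% to 40% is assumed. The standard error of the difference in shares between arms is √(2p(1−p)/63). Suppose also that active patients average 100% and the others 40%, a gap of 60 points.

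| p | SE | 95% range of imbalance | Shift in mean score (× 60) |
|---|---|---|---|
| 0.10 | 0.053 | ±0.105 | ±6.3 points |
| 0.20 | 0.071 | ±0.140 | ±8.4 points |
| 0.40 | 0.087 | ±0.171 | ±10.3 points |

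If active patients average only 67%, the gap is 27 points and the range at p = 0.20 falls to 0.140 × 27 = ±3.8 points. These are limits of chance variation, not typical values. For example, a split of 26% against 14% at p = 0.20 shifts the mean by 0.12 × 60 = 7.2 points, but it is 0.12 / 0.071 = 1.7 standard errors from balance.

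**Step 3: what adjustment could recover.** If activity at inclusion correlates r with a patient's later level, adjustment removes r² of the between-patient variance: 0.3² = 9% and 0.6² = 36%. The range for r is an assumption. Were all the error between patients, the standard error would fall by 1 − √0.91 = 5% to 1 − √0.64 = 20%. Within-patient month-to-month variation is untouched, so the real gain would be smaller.

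**The case against.** The strongest reply is that allocation is randomised, so prior activity is balanced in expectation. Chance imbalance is ordinary sampling variation, already reflected in the unadjusted standard error. There is no bias and no excess type I error, and comparing minutes between arms is valid without a pre-trial baseline. All of this stands. What remains is precision, and protection against an unlucky split.

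Several stronger readings are tempting, and the documents do not support them:

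- *The provider-based exclusion is a flaw.* Siel Bleu delivers the whole control programme and five of the nine experimental sessions (section 4.2), so excluding its former participants is coherent. Leaving other exercise unrestricted is a design choice.
- *A patient already at target scores 100% in either arm, so no effect can show.* The score has no stated cap, so added activity still counts. Lighter exercise below the intensity threshold scores nothing, and no pass/fail threshold is defined.
- *Activity at inclusion is never analysed.* Section 5.2 opens by planning a description of all variables overall and by group, which covers it. Only its use in a model is missing.
- *The criterion 11 model makes the same omission.* There is no criterion 11 model in section 5.2 to fault.
- *The primary result is affected.* The FIQR model includes the D0 score, and the 114 and 126 patients do not depend on this endpoint.

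**Conclusion.** The point holds as a low-severity improvement in precision on a secondary endpoint. Criterion 7 lacks a baseline value, its model has no term for prior activity, and a usable baseline item is already collected. That prior habit alone can score about 67% to 100% follows from the protocol's own formula, under the conditions in step 1. The statistical cost cannot be fixed from the documents: the active share, the score gap and the correlation are all assumed, so the 9% to 36% reduction in between-patient variance and the shifts in step 2 are illustrations only. A difference between arms in criterion 7 would still be a valid randomised comparison, though a less precise one than the collected data allow.

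**What to change.** 1. In the eCRF, record practice at inclusion as minutes per week and type of activity, not as free text.
2. In section 5.2, state that the mixed model for criterion 7 includes minutes per week at inclusion as a prespecified baseline covariate.
3. When an analysis for criterion 11 is written, include the same covariate.

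The cost for criterion 7 is one field format and one sentence. Criterion 11 needs more, because its analysis has still to be described, but that is needed in any case. The downside is that self-reported minutes are imprecise and may not capture intensity, which limits the gain; because they are recorded at inclusion, this does not bias the comparison of arms. The choice should be made before the data are seen: minutes not recorded at entry cannot be recovered reliably, and a covariate added afterwards carries less weight. Eligibility, sample size, visits and the primary FIQR analysis stay as they are.

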4. DESIGN AND STUDY PROCESS

4.1. *EVALUATION METHODS*

The clinical assessments will be carried out by the healthcare team (doctors and nurses) of the CETDs of the participating centres (La Roche Sur Yon, Luçon, Montaigu, CHU Nantes).

These evaluators will be different from physiotherapists or adapted physical activity teachers, regardless of the randomisation arm.

4.2. GENERAL RESEARCH METHODOLOGY

The research has the following characteristics:

- Open study,
- Multicentric (CHD Vendée, CHU Nantes),
- Controlled,
- Of superiority,
- Randomised

Duration of inclusion: 18 months

Duration of participation: 12 months (*including 6 months of adapted physical activity depending on the randomisation arm*)

Duration of the research: 30 months

Randomisation arm :

- **Control group: Classic non-specific management in a common "multipathology" group, with activity trackers:**
 - One face-to-face session per week with the "Siel Bleu" association in the different sites of the Vendée and Loire-Atlantique.
- **Experimental group: Specific telephone coaching for fibromyalgia patients, with activity trackers:**
 - A one-hour face-to-face individual session conducted by the "Siel Bleu" association - Eight telephone coaching sessions in Physical Activity - Health :

- Four 30-minute sessions by the "Siel Bleu" association
- Four 30-minute sessions by physiotherapists from participating institutions

The nine sessions will be spread over 6 months.

Concerning the continuation of physical activity after the end of the experiment (i.e. after M6), the physical activity coaching service could be provided, if the patient so wishes and on his or her initiative, by a private physiotherapist or an adapted physical activity teacher from "Siel Bleu". Similarly, standard care is based on an existing activity currently offered by "Siel Bleu" and can therefore be integrated by the patient who so requests.

4.3. RESEARCH AND ANALYSIS TECHNIQUES

Detailed description of the evaluation parameters

The revised Fibromyalgia Impact Questionnaire (FIQR, Appendix 5) is a self-administered questionnaire to assess the quality of life of the fibromyalgia patient (Burckhardt, Clark, & Bennett, 1991). Composed of 10 items, the first item includes eleven questions rated from 0 to 3 on a Likert scale. Items 2 and 3 ask the patient to indicate the number of days they felt well and the number of days they were unable to work (including housework) due to fibromyalgia symptoms. Items 4 to 10 are horizontal linear scales marked in 10 steps on which the patient rates work difficulties, pain, fatigue, morning fatigue, stiffness, anxiety and depression. The Minimum Clinically Important Difference is 14%. (Bennett et al., 2009). This means that a 14% difference in the FIQR score is clinically important.

The Visual Analogue Scale (VAS) of pain is used to assess the progression of pain (Scott & Huskisson, 1976). . The therapist should explain the use of the scale by presenting the ruler with the extremes: "You have to move the cursor, with no pain on the left and the maximum pain you can imagine on the right". It is marked from 0 to 100 on a ruler, the patient must move a cursor on the side without graduation. The therapist reports the intensity of the pain felt on the graduated side. The Minimum Detectable Change is 11, while the Minimum Clinically Important Difference is 13.7 points out of 100. The evaluation of the pain will be done on the different areas of pain felt by the patient (cervical, limb).

The DN4 questionnaire (Appendix 6) is used for the detection of neuropathic pain. The first part is based on the history, the second on a clinical examination. This questionnaire is administered by the therapist. If the score is greater than or equal to 4/10, the test will be considered positive (Bouhassira et al., 2005).

The isochrony between executed and imagined movement is a test inspired by the work of Moseley (2004) showing an alteration in the temporality of imagined movement in chronic pain patients. Patient positioning: initially, the patient has the upper limb and hand at the side of the body, with the feet 30cm from a table. A magazine is positioned by the operator flat, at the edge and not protruding from the table. First, the operator will ask the patient, "On my 'go' signal, you will take the magazine lying flat in front of you with your dominant hand and bring the limb back along your body at your comfort speed. When you have brought your limb back, you will say "stop". I will stop the clock at your end stop. This movement is to be done twice. The operator will note the 2 times in seconds and hundredths. In a second step, the operator will ask the patient: "At my starting "top", you will, without actually doing it and without moving, imagine taking with your dominant hand the magazine lying flat in front of you

and imagine bringing the limb back along your body at your comfort speed. When you have imagined bringing your limb back, you will say "stop". I will stop the clock at your end stop. This movement is to be done twice. The operator will note the 2 times in seconds and hundredths.

The Hospital Anxiety and Depression scale (HAD, Appendix 8) is a screening instrument for anxiety and depressive disorders. It consists of 14 items rated from 0 to 3. Seven questions relate to anxiety (total A) and seven others to the depressive dimension (total D), thus making it possible to obtain two scores (maximum score for each score = 21) (Zigmond & Snaith, 1983).

The Widespread Pain Index (WPI, Appendix 9) is a score given by the patient according to the number of affected areas (Häuser et al., 2017)

The Symptom Severity Scale (SSS, Appendix 10) is scored by the patient and includes headache, pain, cramp in the abdomen and depression (Häuser et al., 2017)

The percentage of target attainment will be calculated by averaging the attainment of monthly results, compared to clinical practice guidelines from the results recorded by the use of activity trackers

⇒ Duration in minutes per month at least 70% of the theoretical maximum heart rate x100 / 240 minutes
(4 weeks x 60 minutes recommended = 240 minutes)

The percentage (%) and dry mass (in kg) of lean mass will be measured on an impedance scale

Analgesic and painkiller treatments: the consumption of analgesic and painkiller treatments in the week preceding the inclusion visits, M6 and M12 will be collected.

The Tampa Kinesiophobia Index Scale (TSK-CF, Appendix 7) was designed and validated to estimate the level of kinesiophobia present in an individual at the time of assessment, with the aim of adjusting the intervention accordingly, and subsequently assessing whether the intervention has had an effect on this common problem among people with persistent pain. The higher the score, the greater the level of kinesiophobia. A score of 40/68 is considered significant kinesiophobia (Vlaeyen et al. 1995), and the Tampa scale can also be used as a follow-up criterion.

Annex 11 consists of 2 pages: the **EQ-5D** descriptive system and the **EQ** visual analogue scale (EQ VAS).

The descriptive system consists of five dimensions: mobility, personal care, usual activities, pain/discomfort and anxiety/depression. Each dimension has 5 levels: no problem, mild problems, moderate problems, severe problems and extreme problems. The patient is asked to indicate their health

status by ticking the box next to the most appropriate statement in each of the 5 dimensions. The VAS EQ system records the patient's self-assessed health status on a vertical visual analogue scale, where the assessment criteria are entitled "The best health you can imagine" and "The worst health you can imagine". The VAS can be used as a quantitative measure of health outcomes that reflects the patient's own judgement.

The **level of physical activity** between the groups will be measured each month. It will be measured with activity trackers based on the time in minutes per month between 50 and 60, 60 and 70, 70 and 80, 80 and 90, and 90 and 100% of the theoretical maximum heart rate.

The activity trackers are OH1 wristbands from Polar™ (User Manual - Appendix 12). They retrieve, throughout the exercise, the heart rate of the subject thanks to optical sensors. The bracelet is either connected directly to a smartphone to record this frequency, or connectable to a computer in order to retrieve the data written in memory. There is no GPS on the bracelet. Patients will be specifically asked not to activate the GPS mode of the application if they are using a smartphone, in order to comply with the General Data Protection Regulation (GDPR) and data minimisation.

The data is implemented on a private PolarFlow™ cloud account of the subject, accessible by personal private codes. The subject grants a right, retractable at any time and in real time, to transfer the data to PolarFlow for Coach™ (software allowing access to patient training statistics), which can be accessed by therapists and the person in charge of implementing the Case Report Form (CRF), again by personal private codes.

Description of techniques and analyses

In the control group, the adapted physical activity intervention (in a "multipathology" group) consists of one face-to-face session per week. The face-to-face session consists of a ten-minute warmup, followed by forty minutes of *interval training*, and then ten minutes of rest with a flash nap. The *interval training* is interspersed with two minutes of gentle, positive stimulation such as self-massage and targeted infra-painful stretching.

[figure not shown]
In addition, participants are offered the opportunity to log on to the association's website to do a complementary adapted movement activity.

In the experimental group, the specific physical activity intervention consists of an individual faceto-face coaching session carried out by an adapted physical activity teacher (EAPA). The session will consist of therapeutic education in order to teach the basics of physical activity, its interest in the context of fibromyalgia and the rules for its implementation.

Then, the participants will be contacted by telephone eight times over the 6 months of the intervention, four times by the "Siel bleu" EAPAs and four times by the physiotherapists of the participating establishments, in order to collect their motivations, their physical and personal constraints in carrying out a physical activity in line with the recommendations.

The objective is to propose the implementation of specific physical activity(ies) according to the participants' constraints. Physiotherapists and adapted physical activity teachers will have received prior information in order to coordinate the treatment. No paid physical activities will be offered to patients. Thanks to the activity trackers, the physical coaching will be based on the analysis of the participants' activity levels on the dedicated website.

4.4. *SCHEME OF THE STUDY*

